11.3 Exploratory Efficacy Variables

11.3.1 Sleep and Nap Diary by Visit

The change from baseline at 3 weeks of double-blind treatment is analysed in the same model as the change from baseline at 13 weeks. From that model, the adjusted mean change from baseline (and standard error) in TST after 3 weeks of treatment for each treatment group will be calculated and the associated 95% CI for the change presented. Furthermore, the estimated difference (and standard error) between treatments will be estimated, the associated 95% confidence interval presented and the null hypothesis that these means are equal will be tested.

For the TST during open-label treatment the estimated change from baseline (and standard error) will be calculated and associated 95% CI for the change will be presented for each visit. A paired t-test will be performed comparing the mean TST at visit to the baseline mean.

Example SAS code for this analysis is given below:

```
proc means data=tst mean stderr lclm uclm probt;  
  var chg;  
run;
```

These analyses will be repeated for the other sleep variables derived from the Sleep and Nap diary.

A subject is defined as a TST responder if the mean change from baseline in TST is 45 minutes or greater (increase in TST) over the 14 days prior to each scheduled visit. A subject is defined as a sleep latency responder if the mean change from baseline in sleep latency is 15 minutes or greater (reduction in SL) over the 14 days prior to each scheduled visit. Frequency tables of TST response and sleep latency response will be presented by scheduled visit.

For Visits 3 and 4, the TST response rate and sleep latency response rate will be analysed using logistic regression. Subjects without a mean TST (or mean sleep latency) at a visit will be taken to be non-responders in this analysis. The model will include terms for treatment and mean baseline value of TST and sleep latency respectively. From the model the estimated odds of responding will be calculated, as will estimated odds ratios, associated 95% CI and p-values for testing the null hypothesis of the odds ratio being 1.

Example SAS code for this analysis is given below:

```
proc genmod data=resp;  
  class trtp;  
  model resp=trtp base/link=logit dist=bin;  
  lsmeans trtp/diff cl om exp;  
run;
```

The responder analysis will be repeated on all non-missing data. That is, subjects without a mean TST (or mean sleep latency) at a visit will not be included in the analysis.

The time to going to bed will be categorized to the following time slots: < 18:00, 18:00 - < 19:00, 19:00 - <20:00, 20:00 - < 21:00, 21:00 - < 22:00, 22:00 - < 23:00, 23:00 - < 00:00, >= 00:00.

The shift in time to going to bed will be tabulated by scheduled visit for the most frequently occurring time slot over the 14 days at each visit. Where the daily time to going to bed is equally distributed across the time slots, the latest occurring time slot will be selected for inclusion in the shift table.

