3.3 Exploratory Objective

The exploratory objectives of the study are:

- To evaluate the effect of Circadin® 2/5 mg on all sleep variables derived from the Sleep and Nap Diary after 3 weeks of double-blind treatment (Week 5), and after 13, 26, and 39 weeks of open-label treatment (Weeks 28, 41, and 54) as compared to baseline (Week 2)
- To compare the treatment effect of Circadin® 2/5 mg to that of placebo on sleep disturbance as assessed by CSDI score after 3 weeks of double-blind treatment (Week 5), after 13, 26, 39, and 91 weeks of open-label treatment (Weeks 28, 41, 54, and 106, respectively), and at the end of study visit (Week 108) as compared to baseline (Week 2)
- To assess the treatment effect of Circadin® 2/5 mg on children's social functioning at home, in school, and community settings as assessed by the CGAS after 13 weeks (Week 28) of Circadin® open-label treatment as compared to baseline (Week 2)
- To assess the treatment effect of Circadin® 2/5 mg on children's behavior at home and in school as assessed by the SDQ after 13 weeks (Week 28) of Circadin® open-label treatment as compared to baseline (Week 2)
- To assess the level of caregiver's daytime sleepiness (i.e., NOT the child's sleepiness) during the study using the Epworth Sleepiness Scale (ESS) at Weeks 0, 2, 5, 15, 28, 41, 54, 106, and 108
- To assess the level of caregiver's quality of sleep (i.e., NOT the child's quality of sleep) at night during the study using the Pittsburgh Sleep Quality Index (PSQI) at Weeks 0, 2, 5, 15, 28, 41, 54, 106, and 108
- To assess the level of caregiver's well-being (i.e., NOT the child's well-being) during the study using the World Health Organization Well-Being Index (WHO-5) questionnaire at Weeks 0, 2, 5, 15, 28, 41, 54, 106, and 108
- To determine the proportion of children using a maximum of 2 or 5 mg in the Circadin® and placebo groups

- To compare the treatment effect of Circadin® 2/5 mg to that of placebo on children's body mass index (BMI) and Z-score after 3 and 13 weeks of double-blind treatment, and to evaluate the effect of Circadin® 2/5/10 mg compared to baseline, at the end of the open-label period, and at the end of the placebo run-out period

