9.2 Reporting of Phases

Unless otherwise specified, tables will be reported separately for the Double Blind and Open Label phases. Tables reporting the Double Blind phase will be presented by treatment group.

In addition, baseline demographic and history tables will include an Overall column.

Tables reporting data from the Open Label phases will be presented by the original Double Blind treatment group and will also include an 'All Circadin' group. Unless otherwise specified, the two Open Label phases will be reported in the same table. For the main analysis, the Open Label tables will only include data for Visit 5. On completion of the study, the open label tables will be re-run to include all data up to the end of the study.

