9.3 Baseline Derivation

For all efficacy and safety variables, the baseline value will be calculated as the last recorded value prior to the start of randomized treatment.

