10.6 Prior and Concomitant Medications

Concomitant medications recorded during the study will be coded using World Health Organization (WHO)-Drug. Details of concomitant medication will be listed.

Concomitant medications will be summarized according to whether they were being taken pre-study (prior medications) and/or during the study (concomitant medication). Prior medications are any that were being taken prior to the first dose of study medication (medication stop date prior to the first dose of study medication). Concomitant medications are any that were being taken on or after the first dose of study medication. If the start and stop dates of the concomitant medications do not clearly define the period during which a medication was taken, it will be assumed to be a concomitant medication.

Concomitant medications will be assigned to the phase they were taken: Double-Blind, first Open-Label, second Open-Label. If a concomitant medication starts or is ongoing between Visit 2 and Visit 4, it will be assigned to the Double-Blind phase. If a concomitant medication starts or is ongoing between Visit 4 + 1 day and Visit 5, it will be assigned to the first Open-Label phase. If a concomitant medication starts or is ongoing between Visit 5 + 1 day and Visit 8, it will be assigned to the second Open-Label phase. If the start and stop dates of the concomitant medications do not clearly define the phase during which a medication was taken, it will be assumed to be taken across all phases.

Prior and concomitant medications will be summarized by Anatomical Therapeutic Chemical (ATC) level 2 term and preferred term.

Details of non-pharmacological concomitant measures will be listed.

11 Efficacy

Subjects will be classified and summarized by randomized treatment. For all efficacy assessments, the baseline values will be calculated as the last recorded value prior to the start of randomized treatment. Change from baseline values will be calculated as the assessment score minus the baseline value. For questionnaires the change from baseline values will be calculated for each item and total/subscale score as applicable.

All summaries and analyses will be performed on the FAS set. The primary efficacy endpoint and select secondary efficacy endpoints will also be analyzed on the PP set. Analyses looking at the impact missing data on the primary efficacy endpoint will also be performed on the All Randomized set.

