Table 14.2.5.12	Actigraphy Sleep Efficiency Change from Baseline at 13 Weeks Double Blind – MMRM Analysis	FAS Set
Table 14.2.6.1	SND Total Sleep Time Change from Baseline at 3 Weeks Double Blind – MMRM Analysis	FAS Set
Table 14.2.6.2	SND Total Sleep Time and Change from Baseline – Open Label - Descriptive Statistics	FAS Set
Table 14.2.6.3	SND Total Sleep Time Change from Baseline Analysis During the Open Label Phase	FAS Set
Table 14.2.6.4	SND Sleep Latency Change from Baseline at 3 Weeks Double Blind – MMRM Analysis	FAS Set
Table 14.2.6.5	SND Sleep Latency and Change from Baseline – Open Label - Descriptive Statistics	FAS Set
Table 14.2.6.6	SND Sleep Latency Change from Baseline Analysis During the Open Label Phase	FAS Set
Table 14.2.6.7	SND Duration of Wake Change from Baseline at 3 Weeks Double Blind – MMRM Analysis	FAS Set

Table Number	Table Title	Population
Table 14.2.6.8	SND Duration of Wake and Change from Baseline – Open Label - Descriptive Statistics	FAS Set
Table 14.2.6.9	SND Duration of Wake Change from Baseline Analysis During the Open Label Phase	FAS Set
Table 14.2.6.10	SND Number of Awakenings Change from Baseline at 3 Weeks Double Blind – MMRM Analysis	FAS Set
Table 14.2.6.11	SND Number of Awakenings and Change from Baseline – Open Label - Descriptive Statistics	FAS Set
Table 14.2.6.12	SND Number of Awakenings Change from Baseline Analysis During the Open Label Phase	FAS Set
Table 14.2.6.13	SND Longest Sleep Period Change from Baseline at 3 Weeks Double Blind – MMRM Analysis	FAS Set
Table 14.2.6.14	SND Longest Sleep Period and Change from Baseline – Open Label - Descriptive Statistics	FAS Set
Table 14.2.6.15	SND Longest Sleep Period Change from Baseline Analysis During the Open Label Phase	FAS Set
Table 14.2.6.16	SND Total Time in Bed Change from Baseline at 3 Weeks Double Blind – MMRM Analysis	FAS Set
Table 14.2.6.17	SND Total Time in Bed and Change from Baseline – Open Label - Descriptive Statistics	FAS Set
Table 14.2.6.18	SND Total Time in Bed Change from Baseline Analysis During the Open Label Phase	FAS Set
Table 14.2.6.19	SND TST Response – Logistic Regression	FAS Set
Table 14.2.6.20	SND Sleep Latency Response – Logistic Regression	FAS Set
Table 14.2.6.21	SND TST Response – Logistic Regression (Non-Missing Data)	FAS Set
Table 14.2.6.22	SND Sleep Latency Response – Logistic Regression (Non-Missing Data)	FAS Set
Table 14.2.6.23	SND Shift in Time to Bed by Scheduled Visit	FAS Set

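### Open-label change in children randomised to placebo is tested from Week 2, so improvement during 13 weeks of placebo enters an analysis meant to show the effect of Circadin

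*SAP*

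**What the plan says.** SAP 9.3 sets a single rule for all efficacy and safety variables: "the baseline value will be calculated as the last recorded value prior to the start of randomized treatment". The opening of SAP section 11 repeats it for efficacy. In both arms this is the Visit 2 (Week 2) value.

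For TST in the open-label phase, SAP 11.3.1 gives the mean change from baseline with a 95% CI at each visit, and then: "A paired t-test will be performed comparing the mean TST at visit to the baseline mean". The same is done for the other diary variables. SAP 11.3.2 to 11.3.7 carry the approach to CSDI, CGAS, SDQ, ESS, PSQI and WHO-5, and SAP 12.5 to BMI and its Z-score.

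Under SAP 9.2, open-label tables are "presented by the original Double Blind treatment group and will also include an 'All Circadin' group". The output for TST is Table 14.2.6.3, "SND Total Sleep Time Change from Baseline Analysis During the Open Label Phase".

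The objective behind these tests is in SAP 3.3. It begins "To evaluate the effect of Circadin® 2/5 mg on all sleep variables derived from the Sleep and Nap Diary after 3 weeks of double-blind treatment" and goes on to the open-label visits, "Weeks 28, 41, and 54) as compared to baseline (Week 2"). Nowhere does the SAP define a second baseline for children who switch from placebo to Circadin.

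**The concern.** A child randomised to placebo takes placebo for 3 + 10 = 13 weeks after Week 2 and starts Circadin only in the open-label phase. For that child, the change from Week 2 to Week 28 is the sum of the change on placebo and the change after the switch. The test treats the sum as one quantity, and the objective calls it an effect of Circadin. Showing the original arms separately does not help here, because each arm is still measured from Week 2.

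The sponsor expects the placebo part to be above zero: the sample size in SAP 6.1 assumes a gain of 0.27 h on placebo. A significant result in the former placebo group could therefore arise with no effect of Circadin. These results go into the Week 28 clinical study report, which is submitted to support approval (SAP sections 1 and 13).

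**Working it through.** **Inputs.** SAP 6.1: change 0.72 h (SD 0.69) on Circadin and 0.27 h (SD 0.45) on placebo; 45 children per group; 95% power at the 5% level. SAP section 5: 13 weeks of double-blind treatment.

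**The plan's own figure.** Difference = 0.72 − 0.27 = 0.45 h. Average SD = √((0.69² + 0.45²)/2) = 0.5825. The normal approximation gives n = 2(1.960 + 1.645)² × 0.5825²/0.45² = 43.5, so 44 per arm. With the noncentral t distribution, power at n = 45 is 95.1% (Welch) or 95.2% (pooled), and 45 is the smallest n that reaches 95%. The stated 45 reproduces with a two-sided test.

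**Former placebo group, no effect of Circadin.** Suppose that the 0.27 h gain holds to Week 28 and nothing is added after the switch. At n = 45 and SD 0.45 the standard error is 0.45/√45 = 0.0671, so the expected t is 0.27/0.0671 = 4.02. The 95% CI around 0.27 is 0.27 ± 2.015 × 0.0671, or 0.13 to 0.41 h. The rejection probability is that of a two-sided 5% one-sample t-test with noncentrality 0.27√45/SD. The documents give no SD of change at Week 28, so SDs above 0.45 are assumptions:

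| SD (h) | Noncentrality | Rejects, Week 2 baseline | Rejects, Visit 4 baseline |
|---|---|---|---|
| 0.45 | 4.02 | 97.6% | 5% |
| 0.69 | 2.62 | 73% | 5% |
| 0.9 | 2.01 | 50% | 5% |
| 1.2 | 1.51 | 31% | 5% |

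The last column is the nominal level, because the expected change from Visit 4 is zero in this scenario.

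**Former placebo group, full planned effect.** If the whole 0.45 h appears after the switch, the group shows 0.27 + 0.45 = 0.72 h from Week 2 and 0.45 h from Visit 4. The share that arose on placebo is 0.27/0.72 = 37.5%.

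**'All Circadin', no effect of Circadin (45 + 45 children).** From Week 2 the pooled change is 0.27 h, and the test rejects in more than 99.9% of trials at SD 0.45 and 56% at SD 1.2. If each child is instead measured from the last value before the first active dose, the original Circadin arm still shows 0.27 h and the former placebo arm shows 0. The pooled mean is (0.27 + 0)/2 = 0.135 h, and the test still rejects in about 77 to 80% of trials at SD 0.45 and about 18% at SD 1.2. The lower end of the first range allows for the spread between the two arms.

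**The case against.** Several points on the other side stand.

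- **Week 2 is pre-specified.** The objective names it, in the SAP and in Protocol section 4. The test carries out that objective, so this is a choice of reference point, not a contradiction or a derivation error.
- **The analysis is exploratory and uncontrolled.** Protocol 12.8.1 plans only descriptive statistics for open-label diary data. The primary comparison at Week 15 does not depend on it.
- **The placebo gain can be seen elsewhere.** The Week 15 change in the placebo arm is reported with a CI (SAP 11.1.1), change is plotted over time, and open-label tables show the original arms. A careful reader can set the two side by side, apart from dropout between the visits. This makes a misreading less likely but does not change what is tested.

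A reader might infer three stronger things, and the documents support none of them. The first is that a false positive is close to certain. The 97.6% is the top of the range and rests on a planning SD for Week 15 and on a placebo gain that lasts another 13 weeks; the documents establish neither for Week 28. The second is that re-baselining would repair the 'All Circadin' test. It would not, because the original Circadin arm's change from Week 2 also contains a non-drug part. The third is that the change costs nothing. It touches several tables, and a child can enter the Full Analysis Set with a valid Visit 3 mean but none at Visit 4 (SAP 8.4), so a fallback rule is needed.

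**Conclusion.** The concern holds for the exploratory open-label tests in children randomised to placebo. Their change from Week 2 includes whatever happened during 13 weeks of placebo, and the objective presents the comparison as the effect of Circadin. With no effect of Circadin, the TST test rejects in 31% to 97.6% of trials over SDs from 1.2 down to 0.45 h, against a nominal 5%. This assumes n = 45, a placebo gain of 0.27 h as planned, and persistence of that gain to Week 28. On the planning values with a full effect after the switch, 37.5% of the group's change would have arisen on placebo.

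The randomised Week 15 result is unaffected. For the 'All Circadin' row the problem is wider than the baseline: it is an uncontrolled pre-post test in both halves, and only its labelling can be put right.

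**What to change.** In SAP 11.3.1, and through it 11.3.2 to 11.3.7 and 12.5:

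1. For children randomised to placebo, add to the open-label tables the change from the last valid value before the first Circadin dose, with 95% CI and paired test. This is Visit 4, or Visit 3 if Visit 4 is not valid.
2. Keep the pre-specified change from Week 2 as a second line.
3. Label the Week 2 tests, including the 'All Circadin' row, as descriptive, uncontrolled pre-post change and not as an effect of Circadin.

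The Visit 3 and Visit 4 measurements are already scheduled (Protocol Table 5-2), so no new data are needed. The cost is a derived baseline for each variable, extra lines in several tables and the fallback rule. The added line still has no concurrent control, and families know after Visit 4 that the child is on active treatment, so it removes the placebo-phase change but does not isolate a drug effect.

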7 TREATMENTS ADMINISTERED

Children found eligible who do not have documented sleep hygiene training in their history will start a 4-week sleep hygiene and behavioral intervention, which will serve as a wash-out period from any hypnotics with gradual withdrawal during the first 2 weeks and complete withdrawal during the last 2 weeks. Patients will then enter a 2-week SB placebo run-in period. Enough eligible children will be screened for the study to allow for 120 patients to be randomized in a 1:1 ratio to receive Circadin® or placebo at the end of the 2-week SB placebo run-in period, whether they are children who underwent the sleep hygiene and behavioral intervention or not.

Children with a documented history of sleep hygiene and behavioral intervention who are taking prohibited medications will not require additional training and will undergo a 2 week wash-out period before Visit 1 (e.g., Weeks 2 through 0 to wash out melatonin or any other prohibited medications). During these 2 weeks there is no need to complete the sleep and nap diary.

Children with documented history of sleep hygiene and behavioral intervention, who are still found eligible, will enter directly into the 2-week SB placebo run-in period. After the 2-week placebo run-in period, patients who are still found eligible will be randomized in a 1:1 ratio to receive either Circadin® 2 mg or matching placebo for 3 weeks. At the end of the 3-week double-blind period, a decision on dose modification (i.e., an increase to 5 mg) will be made based on predefined criteria ([Section 7.3.1](#)). The double-blind period will continue for another 10 weeks (total 13 weeks) after which Circadin® 2 or 5 mg will be given open-label for another 13 weeks of follow-up to evaluate maintenance of efficacy and safety. At this time point (Week 28), data gathered from both the double-blind and open-label periods will be analyzed. The study will continue with a second opportunity for dose modification according to the same criteria as before (an increase either to 5 mg for patients who are still on 2 mg or to 10 mg for patients who are on 5 mg) after which open-label

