treatment will continue for an additional 78 weeks of follow-up to evaluate maintenance of efficacy and safety. At the end of the Circadin[®] open-label period, patients will undergo a 2-week SB placebo run-out period to assess withdrawal effects. A minimum of 90 children are expected to complete the double-blind and first open-label period. A minimum of 50 children are expected to complete the second open-label safety follow-up period.

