6.1 Sample Size

To achieve 95% power at the 5% level for the primary objective (assuming a change of 0.72 hour in the Circadin® arm and 0.27 hour in the placebo arm and a standard deviation (SD) of 0.69 in the Circadin® arm and 0.45 in the placebo arm), 45 subjects are required per combined group. Therefore, 90 subjects in total are required to complete Visit 5. These estimations are based on previous studies conducted with Circadin®.

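### The open-label efficacy test against the Week 2 baseline cannot show that efficacy is maintained; a paired contrast with Week 15 should be added

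*SAP*

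**What the plan says.** In Protocol Section 7, open-label Circadin after Week 15 "will be given open-label for another 13 weeks of follow-up to evaluate maintenance of efficacy and safety". After Week 28, "treatment will continue for an additional 78 weeks of follow-up to evaluate maintenance of efficacy and safety".

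SAP 11.3.1 gives the open-label analysis of TST: the mean change from baseline with standard error and 95% CI at each visit, and a test. "A paired t-test will be performed comparing the mean TST at visit to the baseline mean." SAP 9.3 defines baseline as the last value before randomised treatment, which is Week 2. The same analysis is repeated for the other diary variables and, in SAP 11.3.2 to 11.3.7, for CSDI, CGAS, SDQ, ESS, PSQI and WHO-5.

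SAP 9.2 has open-label tables shown by randomised arm and for all children on Circadin together. Responder regression covers Visits 3 and 4 only; open-label responder results are frequency tables. No table in SAP 16.1 contrasts an open-label visit with Week 15, and neither document defines a criterion for maintenance.

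The listed objectives differ from Protocol Section 7. In Protocol Section 4 and SAP 3.3, the open-label diary, CSDI, CGAS and SDQ objectives are exploratory and name Week 2 as the comparator.

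**The concern.** For a child randomised to Circadin, maintenance is a question about Week 15: does the benefit reached at the end of double-blind treatment persist? The planned test has a different null hypothesis, namely no change since before treatment.

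The two questions separate because the planning figures include improvement without drug. SAP 6.1 works from "assuming a change of 0.72 hour in the Circadin® arm and 0.27 hour in the placebo arm". A Circadin arm that lost the full difference of 0.72 − 0.27 = 0.45 h would still be expected to sit 0.27 h above Week 2, and a test against Week 2 can detect that remainder.

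The Week 28 results go into the report submitted for evaluation of approval (Protocol 12.3, SAP Section 1). A significant open-label p-value there says little about waning, which is the issue that the purpose in Protocol Section 7 raises.

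**Working it through.** **Inputs (SAP 6.1).** "To achieve 95% power at the 5% level for the primary objective"; mean changes of 0.72 h and 0.27 h; "a standard deviation (SD) of 0.69 in the Circadin® arm and 0.45 in the placebo arm"; "45 subjects are required per combined group"; "90 subjects in total are required to complete Visit 5". Visit 5 is Week 28, so with equal attrition 45 children randomised to Circadin contribute there.

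**Step 1: reproduce the plan's sample size.** By the normal approximation, two-sided 5% and 95% power:

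n = (1.960 + 1.645)² × (0.69² + 0.45²) / 0.45² = 43.5, so 44 per arm.

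With the noncentral t, power is 94.8% at n = 44 and 95.2% at n = 45. The stated 45 per arm is reproduced.

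**Step 2: how often the planned test is significant after loss of benefit.** If a fraction f of the 0.45 h is lost, the true mean change from Week 2 is 0.72 − 0.45f. The noncentrality is that mean divided by SD/√45, with 44 degrees of freedom and a two-sided 5% level.

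| Drug-specific benefit lost | Mean change (h) | SD (h) | Noncentrality | Probability significant |
|---|---|---|---|---|
| 50% | 0.495 | 0.69 | 4.81 | 99.7% |
| 75% | 0.3825 | 0.69 | 3.72 | 95.3% |
| 100% | 0.27 | 0.69 | 2.62 | 72.8% |
| 100% | 0.27 | 0.58 | 3.11 | 86.0% |
| 100% | 0.27 | 0.45 | 4.02 | 97.6% |

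SD 0.58 is √((0.69² + 0.45²)/2). A simulation of 200,000 trials per SD gave 72.9% (SD 0.69) and 97.6% (SD 0.45).

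**Step 3: dependence on n.** SAP 6.2 expects at least 50 children to complete the second open-label period, or 25 per arm if evenly split. At n = 25 the full-loss probability is 47% (SD 0.69) to 82% (SD 0.45). In a pooled group of 90 with a mean change of 0.27 h it is 96% to above 99%.

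**Step 4: what a paired Week 15 to Week 28 contrast would give.** With SD 0.69 at both visits and correlation ρ between the two changes, the SD of the within-child difference is 0.69 × √(2(1 − ρ)). The documents do not give ρ, so a range is shown for n = 45.

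| ρ (assumed) | SD of difference (h) | 95% CI half-width (h) | Power to detect a 0.45 h loss |
|---|---|---|---|
| 0 | 0.976 | 0.293 | 86% |
| 0.3 | 0.816 | 0.245 | 95% |
| 0.5 | 0.690 | 0.207 | 99% |
| 0.7 | 0.534 | 0.161 | >99.9% |

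**Step 5: why 0.45 h should not be the maintenance margin.** If maintenance meant a CI excluding a 0.45 h loss, an observed loss of up to 0.45 − 0.245 = 0.205 h (ρ = 0.3) or 0.45 − 0.161 = 0.289 h (ρ = 0.7) would pass. That is 46% to 64% of the drug-placebo difference.

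**The case against.** The strongest reply is that the test does what the listed objective asks. The open-label objectives are exploratory and use Week 2 as comparator; maintenance appears only in the treatment narrative of Protocol Section 7. Protocol 12.8.1 plans only descriptive statistics for open-label efficacy, so the SAP's test is an addition. This stands. The mismatch is with the stated purpose of the periods, and primary and secondary inference are untouched.

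Second, a reader might infer that the plan would conceal waning. It would not. Means with CIs by randomised arm are tabulated at Week 15 and at each open-label visit, change from baseline is plotted over time, and responder frequencies are shown by visit. A fall from 0.72 h to 0.27 h would be visible. What is missing is a paired estimate with its CI: the separate means may come from different children after dropout, and two separate CIs do not give the CI of the within-child change.

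Third, a reader might infer that the test can hardly fail. With the plan's own Circadin SD it fails in about 27% of trials after total loss; the 98% figure requires giving the Circadin arm the placebo SD. Nor does the range of 73% to 98% carry over to other outcomes or to Weeks 41 and 54.

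Fourth, no passage says that a significant open-label p-value will be presented as maintained efficacy. That is a risk of interpretation, not a stated intention.

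Finally, a Week 15 contrast is itself uncontrolled. Week 15 is when double-blind treatment gives way to open-label treatment, so changed expectations may alter parent-reported outcomes. This limits the added analysis but does not make the Week 2 test informative about maintenance.

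**Conclusion.** The point holds as a limited one. The only planned open-label efficacy test cannot distinguish maintained from lost benefit, although Protocol Section 7 makes maintenance a purpose of both periods. For TST at Week 28 in children randomised to Circadin, it would be significant about 73% of the time (SD 0.69), and up to 98% if the SD were 0.45, after loss of the entire 0.45 h difference.

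These figures assume 45 completers in that arm, the planning means and SDs, and that losing all drug-specific benefit means falling to the placebo arm's assumed change of 0.27 h. They apply to that outcome, arm and visit only. The documents do not support reading this as a conflict with the listed objectives or as a threat to the primary analysis. It is an inexpensive improvement to an exploratory analysis.

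**What to change.** In SAP 11.3.1, for children randomised to Circadin:

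- Add the paired mean change from Visit 4 (Week 15) to Visit 5 (Week 28), with 95% CI, for the diary variables, CSDI, CGAS and SDQ.
- Extend it to Weeks 41 and 54 for the diary variables and CSDI only. Protocol Table 5-2 does not schedule CGAS or SDQ after Visit 5.
- Report it as an estimate with its CI, and do not use the full 0.45 h as a maintenance margin.
- State that the test against Week 2 describes change since baseline and is not by itself evidence of maintained efficacy.

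The cost is SAP wording and one more table per outcome; no new data are needed. Three limitations should be stated with the results: only children with both visits contribute; the change to open-label treatment at Week 15 may alter parent-reported outcomes; and dose increases at Visit 5 mix dose with time at the later visits.
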